Sponsor	The sponsor is the party that commissions the organisation or performance of the research, for example a pharmaceutical company, academic hospital, scientific organisation or investigator. A party that provides funding for a study but does not commission it is not regarded as the sponsor, but referred to as a subsidising party.
SUSAR	Suspected Unexpected Serious Adverse Reaction
UAVG	Dutch Act on Implementation of the General Data Protection Regulation; in Dutch: Uitvoeringswet AVG
WMO	Medical Research Involving Human Subjects Act; in Dutch: Wet Medisch-wetenschappelijk Onderzoek met Mensen

SUMMARY

Rationale: Although there have been major advances in (personalized) stroke treatment in the last decade, the need for prevention of stroke remains critical. Prevention of recurrent stroke is currently primarily organized through management of cardiovascular risk factors including lifestyle, hypertension and atrial fibrillation (AF). To improve the cardiovascular risk management of stroke patients, more frequent measurements of blood pressure and heart rhythm are essential. In addition, actively engaging the patient with their own recovery could lead to an improved lifestyle. Recent studies have shown telemonitoring of patients can improve care, help with prevention of disease, and reduce healthcare costs, whilst keeping the patient more engaged with their disease.

The LUMC “Box” has shown to effectively monitor blood pressure of patients after myocardial infarction with equal results and patient satisfaction rates compared to standard care with less physical contact moments. We plan to use this framework for improving post-stroke care by introducing more frequent blood pressure and heart rhythm measurements. Additionally, we will provide more information around lifestyle improvement and have the patient actively engage with their weight and physical activity.

In this study we will be evaluating the technical feasibility and clinical implementation of the home-based self-measurements using the Box in a post-stroke pilot setting: the Stroke Box. The results will be used as a basis for the power calculation for a future randomized clinical trial on the effect of the Box on hypertension treatment and AF detection.

Objective: The overall aim of this pilot is to evaluate the technical feasibility and clinical implementation of the Stroke Box by evaluating user experience and hypertension management. The primary objective is gathering data on blood pressure management for power calculation for a future randomized clinical trial where the effect of the Stroke Box on hypertension management and AF detection will be studied. The secondary objectives will be gathering and evaluating data on heart rhythm, weight and activity of patients using the Stroke Box, evaluating the technical- and workflow implementation for healthcare professionals, evaluating the self-management and user-experience of patients, assessing the patient adherence to the self-measurements and pharmacotherapeutic prophylactic therapy, and evaluating the correct functioning of the IT infrastructure, hardware and LUMC Care app, and to assess the correct use of all stakeholders involved in the eHealth support and telemonitoring with the Stroke Box.

Study design: This study is a prospective cohort study to evaluate the implementation of the Stroke Box and gather data. For the first 5 patients we will mainly evaluate the technical procedures of the study in addition to the other objectives. For the remainder, we will be gathering data on blood pressure management, patient engagement and have a user-based

evaluation of the eHealth infrastructure during a six-month follow-up period. We will do evaluations of the collected data based on a before-after comparison of blood pressure and questionnaire results.

Study population: Patients admitted for a TIA, ischemic or haemorrhagic stroke in the LUMC. We will include 55 patients in total of which in the first 5 patients we specifically focus on testing and evaluating the technical feasibility.

Intervention (if applicable): The Stroke Box will contain a blood pressure monitor, weighting scale, single-lead ECG wristwatch with activity tracking and associated apps. Patients are asked to measure the associated factors on a weekly basis. In addition, all patients will be asked to fill in a questionnaire at the start and the end of the study. Patients will participate for 6 months in the pilot.

Main study parameters/endpoints: The primary objective of this study is the gathering of data on blood pressure management as a basis for power analysis in future trials. The secondary objectives will be gathering and evaluating data on heart rhythm, weight and activity of patients, evaluating the technical- and workflow implementation for healthcare professionals, evaluating the self-management and user-experience of patients, assessing the patient adherence to the self-measurements and pharmacotherapeutic prophylactic therapy, and finally evaluating the technical feasibility for all stakeholders.

Nature and extent of the burden and risks associated with participation, benefit and group relatedness: Patients are asked to measure weight, blood pressure and heart rhythm on a weekly basis, which takes approximately 5-10 minutes. All devices used by patients for personal management in this study are non-invasive, easy-to-use, CE marked and electrically safe within their intended use. Using the devices comes with very limited risks. This study has several potential benefits for patients. First, patients can measure their own blood pressure, heart rhythm and weight, which can give them more insight in their own health and may spark a healthier lifestyle (the so-called 'patient empowerment'). Furthermore, these data give the GP or GP nurse more insight in the health status of patients, potentially leading to better cardiovascular risk management and hypertension control. Finally, the regular ECG measurements might help in detecting occult AF in patients at risk for AF.

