2. OBJECTIVES

Primary Objective:

- Gathering data on self-measured blood pressure and AF detection of patients using the Stroke Box as a basis for power analysis of a future randomized controlled clinical trial and performing a quality assessment of the collected data.

Secondary Objectives:

- Gathering data on self-measured heart rhythm, weight and activity of patients using the Stroke Box, and performing a quality assessment of the collected data.
- Evaluation of the potential change in self-management, patient engagement and user experience of the patients using the Stroke Box, using questionnaires.
- Assessment of patient adherence to the self-measurements and pharmacotherapeutic prophylactic therapy, using questionnaires.
- To evaluate our implementation of the IT infrastructure, hardware and LUMC Care app, and to assess the correct use of all stakeholders involved in the eHealth support and telemonitoring with the Stroke Box. The devices themselves and their functioning are not a subject of research.
- User based evaluation of the technical – and workflow implementation for healthcare professionals using the Stroke Box, using questionnaires.

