8.1.2 Secondary study parameters/endpoints

The secondary objectives of this study are:

- Gathering data on self-measured heart rhythm from the Withings Move ECG as an indicator of atrial fibrillation, weight and activity of patients using the Stroke Box, and performing a quality assessment of the collected data as assessed by regularity of assessments and frequency of occurrence of measurement error.
- The potential change in self-management of the patients due to the Stroke Box as measured through changes in lifestyle. This will be measured using changes in results from questionnaires on physical activity and healthy lifestyle intentions taken at the start and at the end of the study and the development of weight of the patient.

For the evaluation of physical activity we will adapt the Short Questionnaire to Assess Health enhancing physical activity questionnaire (SQUASH)²⁰, for the evaluation of healthy lifestyle intentions we will use the Healthy Lifestyle Intentions (HLI) questionnaire.

The evaluation of the self-management of the patient will be assessed by the Reach Efficacy Adoption Implementation Maintenance (RE-AIM) model with a mixed model evaluation based on the normalization process theory.²¹⁻²³

- Assessment of the patient adherence to the self-measurements and pharmacotherapeutic prophylactic therapy, using the Partners In Healthcare (PIH) questionnaire which measures how the patient manages his/her own disease. At the end of the study a comparison will be made between the group of patients who used the IkOefenZelf platform and those who did not.
- The technical implementation and patient adherence to the self-measurements by analysing how often they performed the measurements, if they experienced any problems as measured through the questions they asked during the study, and how they experienced the overall implementation as measured through the mHealth App Usability Questionnaire (MAUQ)²⁴ at the end of the study.
- User based evaluation of the technical – and workflow implementation for the GPs using the Stroke Box as evaluated with the Acceptability of Intervention Measure (AIM), Intervention Appropriateness Measure (IAM), and Feasibility of Intervention Measure (FIM)²⁵ questionnaires for healthcare professionals.

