8.1.3 Other study parameters

- Age
- Sex
- Body Mass Index
- Cardiovascular risk factors including medication (hypertension, diabetes mellitus, hypercholesterolemia, smoking, alcohol)
- Cardiovascular medical history (atrial fibrillation, stroke including all subtypes, heart failure, myocardial infarction)
- Stroke specific (stroke related disabilities as assessed by the National Institutes of Health Scale Score at discharge, modified Rankin Scale at discharge)
- The GP practice where the patient is registered and how the self-measurements are shared with the GP (i.e. via Medical Dashboard or manually)

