When the patient records abnormal measurements indicating a high or rapid increase in blood pressure, they are instructed to not immediately contact a physician. This, in order to reduce the amount of (unnecessary) additional consults with the GP. Specifically, the patient is instructed to only contact their GP if they record a systolic blood pressure >140 mmHg for three days in a row or take up immediate contact if they record a systolic blood pressure >180 mmHg which is cause for immediate adjustment of the hypertension medication according to the NHG guidelines.

In addition to the standard care where patients receive a 48-hour Holter, patients who are suspected to have atrial fibrillation because of e.g. a cryptogenic stroke will be asked to also perform home measurements of their heart rhythm on a daily basis. They are recommended to do this on the same day and time every day. They will be very clearly instructed that their ECG measurements are not monitored regularly and that they should contact 112 in case of emergency.

After a measurement the Withings Move ECG performs a standard analysis resulting in either "normal", "inconclusive" or "atrial fibrillation". If their ECG smartwatch shows "atrial fibrillation" they are instructed to contact a dedicated nurse specialist who will check the measurements and refer them to the cardiology outpatient clinic if necessary. If the result is "inconclusive", the patient is asked to repeat the measurement the next day. When the repeated measurement shows "inconclusive" again or when the measurement shows a warning for potential AF, they are instructed to also contact the dedicated nurse specialist who will contact the patient for further follow-up if necessary. It should be noted that a clinical diagnosis will never be based on the self-measurements. Instead they serve as an early screening tool leading to patients with potential AF to be invited to the cardiology outpatient clinic to receive a diagnosis via the standard Holter measurement.

All ECG data are collected after the study and re-inspected by a PhD researcher of the LUMC for AF and in case of doubt checked again by an experienced cardiologist. In case of suspected AF, the patient is invited to the cardiology outpatient clinic. As 87% of stroke patients have ischemic strokes¹⁶ and about a

third of those have cryptogenic strokes, we expect to find cryptogenic strokes in about 29% of the LUMC stroke population.¹⁷

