11.4 Benefits and risks assessment, group relatedness

Additional to their usual care patients will be asked to fill in several questionnaires at the start and end of the study and will measure their blood pressure, activity, weight and potentially their heart rhythm regularly. The devices used in the pilots are non-invasive and easy to use.

Potential benefits of participating in this study are both short and long term. In the short term, patients may develop an increased awareness with regards to their health, leading to an improved lifestyle. This, on the long term may reduce the risk of cardiovascular disease by a possible positive change in lifestyle.

A major potential risk is the false sense of safety created by the self-measurements. Patients may, incorrectly, assume that a physician constantly monitors their wellbeing and therefore not directly seek treatment when this is required. We will therefore explicitly make sure this is avoided by indicating this at inclusion, in the patient information form. In

the Withings Healthmate app, a notification is also included by default indicating that the patient's data is not monitored by a physician.

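### The Summary and section 8.3 set different ECG schedules, and no planned analysis yields the AF detection rate that the pilot should supply for the future power calculation

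*Combined protocol and SAP*

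**What the plan says.** **Who records ECGs, and how often**
- Summary, burden paragraph: "Patients are asked to measure weight, blood pressure and heart rhythm on a weekly basis". The Summary's intervention paragraph, after listing the Box contents including the ECG watch, adds "Patients are asked to measure the associated factors on a weekly basis". Neither limits this to a subgroup.
- Section 8.3 names only weight and blood pressure as weekly. ECGs are requested separately from patients with suspected AF, who "will be asked to also perform home measurements of their heart rhythm on a daily basis". Cryptogenic stroke is given only as an example of a reason for suspicion.
- Section 11.4: patients "will measure their blood pressure, activity, weight and potentially their heart rhythm regularly".
- Section 4.4 builds its expected number of AF cases on the cryptogenic share, about 29%.

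**The status of AF detection**
- Section 2, primary objective: "Gathering data on self-measured blood pressure and AF detection of patients using the Stroke Box as a basis for power analysis".
- Section 4.4 uses the expected two to three AF cases as part of the argument that 55 patients is the minimum.
- Section 8.1.1 covers blood pressure only. Section 8.1.2 places among the secondary parameters "self-measured heart rhythm from the Withings Move ECG as an indicator of atrial fibrillation".
- Section 10.1 analyses the mean number of heart rhythm measurements per week. No part of section 10 mentions an AF proportion.

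**What could count as AF**
- Section 6.4 accepts that the watch may give false positive or false negative results.
- Section 8.3 describes a watch result, a nurse's check, referral to cardiology with a Holter, and re-inspection of all ECGs after the study. It states that "a clinical diagnosis will never be based on the self-measurements".
- AF history is recorded under section 8.1.3. Known AF is not an exclusion criterion in section 4.3.

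**The concern.** The pilot is meant to hand two quantities to the future trial: one on blood pressure and one on AF detection. For the second, a reader who follows the plan meets three gaps.

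1. The ECG schedule depends on which section is followed. Daily recording gives seven times as many chances to catch intermittent AF as weekly recording, and the group recording is either everyone or a subgroup. The yield and the adherence target both change with that choice.
2. The quantity itself is not analysed. A mean number of ECGs per week does not say how many patients had AF.
3. If the team computed a yield anyway, the plan does not say which step in the pathway makes a patient a case, who belongs in the denominator, or whether patients with known AF are left out.

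With only two or three cases expected, a single case counted differently moves the estimate a long way.

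**Working it through.** **1. The plan's own expected count (section 4.4)**

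Inputs: 55 patients; 87% ischaemic; one third of those cryptogenic; occult AF in 9% to 16% of cryptogenic stroke.
- Cryptogenic share: 0.87 / 3 = 0.29
- Cryptogenic patients: 55 × 0.29 = 15.95, about 16
- Expected AF cases: 15.95 × 0.09 = 1.4 and 15.95 × 0.16 = 2.6

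The stated two to three is reproduced if both ends are rounded up; to the nearest whole number the range is one to three. The figure depends on the cryptogenic denominator: the same rates applied to all 55 would give 55 × 0.09 = 5.0 to 55 × 0.16 = 8.8 cases. With 16 patients at risk, the binomial probability of at least two cases is 0.43 at 9% and 0.75 at 16%.

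**2. The same cases over different denominators (exact 95% intervals)**

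The size of the suspected-AF group is not given. Taking it as the cryptogenic 16 is an assumption.

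| Cases | Of 16 | Of 55 |
|---|---|---|
| 2 | 12.5% (1.6% to 38.3%) | 3.6% (0.4% to 12.5%) |
| 3 | 18.8% (4.0% to 45.6%) | 5.5% (1.1% to 15.1%) |

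The ratio is 55 / 16 = 3.4.

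**3. Mean ECGs per week at full adherence, averaged over all 55**
- Summary: 55 × 1 / 55 = 1.0
- Section 8.3 with 16 patients recording daily: 16 × 7 / 55 = 2.0

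Taking six months as 26 weeks, one patient would record 26 ECGs on the weekly schedule and 26 × 7 = 182 on the daily one.

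**4. Range for the assumed group size**

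| Patients asked for daily ECGs | Two cases as a share of that group | Mean ECGs per week over all 55 |
|---|---|---|
| 10 | 20.0% (2.5% to 55.6%) | 70 / 55 = 1.3 |
| 16 | 12.5% (1.6% to 38.3%) | 112 / 55 = 2.0 |
| 30 | 6.7% (0.8% to 22.1%) | 210 / 55 = 3.8 |
| 48 (all ischaemic, 0.87 × 55) | 4.2% (0.5% to 14.3%) | 336 / 55 = 6.1 |

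The denominator effect shrinks as the group grows, while the gap between the two adherence targets widens.

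**5. Tracing AF detection through the plan**

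Primary objective (section 2), then part of the sample size argument (4.4), then absent from the main parameter (8.1.1), then a secondary parameter expressed as a watch signal (8.1.2), then a recording frequency (10.1). The chain ends without a proportion.

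**The case against.** The strongest reply is that the body of the protocol is coherent. Sections 4.4, 8.3 and 11.4 all describe ECGs in a subgroup, and section 8.3 repeats the 29% figure at the end of its ECG text. On that view the Summary is merely compressed, and a descriptive pilot needs no formal AF endpoint. With two or three events, the estimate will be poor whatever the denominator, and the intervals above overlap widely.

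Much of this stands. The conflict is between the Summary and the body, and sections 4.4 and 11.4 do not add to it. The gain in precision from fixing the denominator is small. But the Summary does state a schedule for all patients that section 8.3 does not contain, and a pilot that promises an input to a power calculation must at least define and report it.

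A reader might also infer more than the documents support:
- *That the plan confuses watch alerts with AF diagnoses.* It does not. The care pathway in section 8.3 keeps them apart, and section 4.4 speaks of occult AF found after discharge. What is missing is the case definition for analysis.
- *That alerts and confirmed cases will differ several-fold.* The documents give no false positive rate, so no size can be put on this. The 3.4-fold figure concerns the denominator alone.
- *That patients with known AF will inflate the alerts.* They are eligible and could do so. Under section 8.3, however, ECGs are asked of patients with suspected AF, so a patient with known AF need not be asked.
- *That everyone records weekly and a subgroup also daily.* No section states this combination, so no adherence target should be derived from it.

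**Conclusion.** The point holds for the schedule, the status of AF detection and the analysis. The plan as written contains two ECG schedules, gives a mean ECG frequency with no fixed target, and provides no analysis that produces the AF rate promised in section 2. It should be corrected before the pilot's AF data are used to size a trial.

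On the assumption that 16 of 55 patients record ECGs, the choice of denominator moves the yield from two cases between 12.5% and 3.6%, and the full-adherence mean is 2.0 or 1.0 per week. The 16 rests on the plan's general stroke figures. It may not fit a cohort that also enrols TIA and requires hypertension, and section 8.3 leaves membership of the ECG group open. The blood pressure objective is unaffected. No view is taken on which ECG schedule is right; the sections must be reconciled.

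**What to change.** 1. Reconcile the Summary with sections 8.3 and 11.4 so that one ECG schedule is stated, including who is asked to record.
2. Give AF detection the same status, primary or secondary, in the Summary and in sections 2, 8.1 and 10.
3. In section 10.1, add an AF yield. Denominator: patients without AF history who were asked to record ECGs, shown by suspected-AF group if others also record. Report three separate counts: patients with a device alert, patients with AF on the re-inspected ECGs, and patients with clinically confirmed new AF. Give exact intervals and say which count will feed the power calculation.
4. Compute ECG frequency among the patients asked to record, against the number of recordings that the schedule requires of them.

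**Cost.** Mostly wording. AF history and ECGs are already study data. The outcome of the cardiology referral is not listed as a study parameter, so it must be added. It also needs a stated cut-off date, because re-inspection takes place after the study and a resulting clinic visit could fall after the last patient's last visit, which section 12.5 defines as the end of the study. The confirmed count may be smaller than the alert count, so the pilot may have fewer cases to report.

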1. INTRODUCTION AND RATIONALE

Although there have been major advances in (personalized) stroke treatment in the last decade, the need for prevention of stroke remains critical.¹ Currently in the Netherlands, prevention of stroke is primarily performed by the general practitioner (GP) in their cardiovascular risk management (CVRM). Lifestyle management, blood pressure regulation and cholesterol lowering interventions are the cornerstones in prevention of neuro- and cardiovascular disease. Resources - primarily time – are, however, limited in healthcare which leaves room for improvements to the CVRM. Post-stroke CVRM consists of regular visits to the GP or GP nurse where blood pressure, lifestyle and medication adherence is monitored. Although these visits are regular, a recurring problem is that these measurements are not always accurate. A patient may have taken his or her medication just before the measurement, is in a different and potentially stressful environment or might be fatigued from travel all of which can affect blood pressure. In addition to hypertension, atrial fibrillation (AF) is also an important risk factor.² However, studies show AF is missed during a hospital admission in a substantial number of stroke patients.³

Recent studies have shown telemonitoring of patients can improve healthcare. A study in patients with hypertension showed that increased monitoring and subsequent treatment led to a better controlled blood pressure in patients who were treated for hypertension.⁴ Moreover, the application of telehealth reduces healthcare costs by a combination of preventing unnecessary hospitalisation, clinic visits and use of medical resources and by offering a solution for the demand of an effective chronic disease management with focus on patient-centered care.⁵⁻⁹

Over the past five years, smartphone compatible detectors of neuro- and cardiovascular disease parameters have been released on the consumer market. Examples of these wearable eHealth tools include ECG monitors, blood pressure monitors, activity trackers and fat percentages monitors. These monitors have often been validated and are CE-marked for use in the European Union within their intended use. Therefore, wearable eHealth technology is a promising tool to improve patient monitoring and patient safety.

Studies also show that home monitoring of blood pressure leads to more accurate measurements, reflecting actual blood pressure better than GP practice measurements.¹⁰ Even for patients with poorly controlled blood pressure in primary care, home monitoring can significantly reduce the blood pressure.¹¹ Using a wearable ECG monitor, blood pressure sensor, activity tracker and weight scale at-home monitoring of stroke-risk is made well accessible. The thereby improved CVRM could hence improve chances for prevention of a recurrent stroke and also reduce the costs of unnecessary GP visits.

At the Leiden University Medical Center (LUMC) “The Box” initiative is getting widely adopted, providing a solid foundation for expanding to other areas of the clinic.¹² It is one of the three pillars of the LUMC2.0 digital strategy as it can effectively support patients by

giving them more insight into their own health status. Moreover, results from earlier “Box” studies, such as the “Cardio Box” for care after myocardial infarction, showed that patients were very satisfied with the care they received and that the blood pressure regulation in patients with the Box was as good as in regular care. This “Box” has many similarities to the project described here giving us confidence that the implementation of the Stroke Box can improve care. Additionally, “The Box” was cost effective with increased efficiency of care.¹³ We therefore selected this well tested workflow as a basis for our patient-centered eHealth approach for improving post-stroke care.

Before performing a randomized controlled clinical trial investigating the effects of the self-measurements on blood pressure and heart rhythm with the Stroke Box, we will run a pilot on a small group of patients.

For the first 5 patients in this pilot we mainly test the technical feasibility of the eHealth infrastructure and evaluate the stakeholder experience. This is essential because this study differs from previous Box projects in several ways. First, our patient population is expected to be generally older compared to previous studies and will likely have substantial physical or cognitive disabilities as a result of the stroke which may lead to a reduced adaptation to the self-monitoring and use of eHealth devices. Second, this is the first Box-related project in which the Box is used to facilitate the transfer between hospital and home care. Therefore the transfer to and communication with GPs, i.e. feasibility of setting up a collaboration with multiple practices, will have to be evaluated.

In the remaining 50 patients, we evaluate the clinical implementation where we will collect data as a basis for the power calculation in the future trial. In this protocol we will describe the setup of this pilot study.

